**Rationale:**

The intent of this amendment is to clarify the blinding of central laboratory test results during the double-blind treatment period and provide guidance in obtaining local lipid panels.

**Table 1. Summary of Amendment Changes**

Section	Text in Protocol	Amended Text	Rationale for Change
Header	Global	Replace: 25 August 2016 With: 08 February 2017	Update to new date.
Front page		Add: Amendment 3 Date 08 February 2017	Update to new date.
Investigator's agreement	Paragraph 1	Replace: I have read the attached protocol entitled "A RaNdomized Double-blInd Placebo ConTrolled Study Characterizing THe Effects of PCSK9 Inhibition On Arterial Wall inflammation in Patients with Elevated Lp(a) (ANITSCHKOW)", dated 25 August 2016, and agree to abide by all provisions set forth therein. With: I have read the attached protocol entitled "A RaNdomized Double-blInd Placebo ConTrolled Study Characterizing THe Effects of PCSK9 Inhibition On Arterial Wall inflammation in Patients with Elevated Lp(a) (ANITSCHKOW)", dated 08 February 2017 , and agree to abide by all provisions set forth therein.	Update to new date
Section 7.5	Paragraph 1	Replace: All screening and on-study laboratory samples will be processed and sent to the central laboratory with the exception of serum pregnancy after screen 1 visit (Section 7.5.1). With: All screening and on-study laboratory samples will be processed and sent to the central laboratory with the exception of serum pregnancy after screen 1 visit (Section 7.5.2 ).	Update to new Section number.

Page 1 of 2

**Table 1. Summary of Amendment Changes**

Section 7.5	Page 34 - 35	
Add:
 
7.5.1 Blinding of Laboratory Test Results
 
In order to protect the blinding of the double-blind treatment period, the following labs will be blinded to the Amgen study team and site staff from post-day 1 until unblinding of the clinical database and not reported to sites: fasting lipid panel (see Table 2), Lp(a), OxPL/ApoB, IL-6, hsCRP, and Lp(a) isoform distribution.
 
In addition, investigators and staff involved with this trial and all medical staff involved in the subject's medical care should not perform non-protocol testing of these analytes during a subject's study participation and until at least 12 weeks after the subject's last administration of IP or the end of the study, whichever is later, to prevent unblinding the patient and site to the treatment assignment, except when it is medically necessary.
 
If a local lipid panel is drawn, all reasonable steps must be undertaken to avoid informing the subject and study personnel of the results.
	Provide guidance in obtaining local lipid panels and clarify the blinding of central laboratory test results during the double-blind treatment period.
Section 7.5	Page 35	
Replace:
 
7.5.1 Serum Pregnancy Test
 
With:
 
7.5.2 Serum Pregnancy Test
	Update section numbering

Page 2 of 2

## Rationale:

The protocol was amended to change the age of the patients included in the study from  $\ge 45$  to  $\ge 50$  years to meet the radiation dose limit required by the Dutch ethics committee. In addition, the study schema was updated for clarity. The primary and exploratory endpoints were reworded for clarity and the methods of analysis for the primary endpoint further detailed.

**Rationale:**

- The protocol has been amended to provide clarification to minimize the risk of confounding the primary endpoint with prior therapies targeting Lp(a), an exclusion criterion has been added to exclude subjects with exposure to therapies targeting Lp(a) within the 12 months prior to Screening.
- The protocol was amended to clarify the timing and method of pregnancy testing. No additional testing or change in testing has been introduced. The ICF reflects this clarification in pregnancy testing.
- The protocol was amended to include additional detail regarding the volume of blood drawn to satisfy the existing protocol-specified laboratory testing. No additional testing has been introduced. The informed consent form (ICF) reflects this additional level of detail regarding blood volume.

Appendix B. Technical Analytical Study Week Assignments.....	25
Appendix C. Reference Values/Toxicity Grades	26

Table of Abbreviations

Abbreviation or Term	Definition/Explanation
AE	Adverse event
AHA	American Heart Association
AI	Autoinjector
ALT	Alanine aminotransferase
ANCOVA	analysis of covariance
ApoA1	Apolipoprotein A-1
ApoB	Apolipoprotein B
AST	Aspartate aminotransferase
CHD	Coronary Heart Disease
CK	Creatine phosphokinase
CSR	Clinical study report
CT	Computed tomography
CTCAE	Common Terminology Criteria for Adverse Events
DBP	Diastolic blood pressure
DRE	Disease-related event
eCRF	Electronic Case Report Form
EOIP	End of Investigational Product
EOS	End of study (for individual subject)
FAS	Full analysis set
FDG	Fluorodeoxyglucose
FDG-PET/CT	Fluorodeoxyglucose-positron emission tomography/computed tomography
HDL-C	High-density lipoprotein cholesterol
hsCRP	High sensitivity C-reactive protein
IP	Investigational product
IPD	Important protocol deviation
IVRS	Interactive Voice Response System
IWRS	Interactive Web Response System
LDL-C	Low-density lipoprotein cholesterol
LFT	Liver function test
Lp(a)	Lipoprotein(a)
MDS	Most diseased segment
MedDRA	Medical dictionary for regulatory activities
NCEP	National Cholesterol Education Program
OxPL	Oxidized phospholipids

Abbreviation or Term	Definition/Explanation
PCSK9	Proprotein convertase subtilisin/kexin type 9
PK	Pharmacokinetic
QM	Monthly (Every 4 weeks)
QD	Once a day
SAE	Serious adverse event
SAP	Statistical analysis plan
SBP	Systolic blood pressure
SC	Subcutaneous
SCIPD	Dose date of SC investigational product
SD	Standard deviation
TBR	Target-To-Background Ratio
TEAE	Treatment-Emergent Adverse Event
ULN	Upper limit of normal
VLDL-C	Very low-density lipoprotein cholesterol

1. Introduction

The purpose of this Statistical Analysis Plan (SAP) is to provide details of the statistical analyses that have been outlined within the protocol amendment 3 for evolocumab Study 20130293 dated 8 February 2017. The scope of this plan includes the final analysis that are planned and will be executed by the Biostatistics department unless otherwise specified.

2. Objectives

2.1 Primary

To evaluate the effect of evolocumab on arterial wall inflammation, as measured by percent change from baseline in target-to-background ratio (TBR) of an index vessel by fluorodeoxyglucose-positron emission tomography/computed tomography (FDG-PET/CT) at week 16 in subjects with baseline lipoprotein (a) [Lp(a)] \geq 50 mg/dL and low density lipoprotein-cholesterol (LDL-C) \geq 100 mg/dL.

2.2 Secondary

- To evaluate the effect of evolocumab on Lp(a), as measured by percent change from baseline at week 16 in subjects with baseline Lp(a) \geq 50 mg/dL and LDL-C \geq 100 mg/dL
- To evaluate the effect of evolocumab on LDL-C, as measured by percent change from baseline at week 16 in subjects with baseline Lp(a) \geq 50 mg/dL and LDL-C \geq 100 mg/dL
- To evaluate the effect of evolocumab on Apolipoprotein B (ApoB), as measured by percent change from baseline at week 16 in subjects with baseline Lp(a) \geq 50 mg/dL and LDL-C \geq 100 mg/dL

2.3 Safety

To evaluate the safety of evolocumab in subjects with baseline Lp(a) \geq 50 mg/dL and LDL-C \geq 100 mg/dL

2.4 Exploratory

CCI

3. Study Overview

3.1 Study Design

This is a phase 3b, multi-center, double-blind, randomized, placebo-controlled study evaluating the effect of evolocumab on arterial wall inflammation as measured by FDG PET/CT following 16 weeks of treatment in subjects with elevated levels of Lp(a).

Eligible subjects will have hyperlipidemia with Lp(a) \geq 50 mg/dL and LDL-C \geq 100 mg/dL. In addition, the subjects must have TBR max $>$ 1.6 on FDG PET/CT in order to qualify for enrollment. If subjects are on statin or other lipid-lowering therapy (not required to participate in this study), they must be on a stable dose for at least 8 weeks prior to screening and during the entire time of screening and throughout the study.

The study will include 2 screening visits (screen 1 and screen 2) during the screening period, which will be a maximum total of 56 days. Subjects will be randomized 1:1 into 2 treatment groups: evolocumab 420 mg QM SC or placebo QM SC. Randomization will be stratified for balance by baseline background statin therapy (on statin vs not on statin) and by screening Lp(a) ($<$ 175 mg/dL or \geq 175 mg/dL). The treatment period will be 12 weeks in duration with study visits every 4 weeks. At the end of study (EOS) visit at week 16, FDG PET/CT will be conducted.

3.2 Sample Size

At present, PCSK9 inhibitors have not been evaluated for their ability to lower arterial wall inflammation. Therefore, we have used an efficacy study with atorvastatin aimed to lower LDL-C and arterial wall inflammation for our sample size estimation ([Tawakol et al, 2013](#)). The planned sample size is 120 subjects (60 in evolocumab and 60 in control). Based on [Tawakol et al, 2013](#), we make an assumption that each 10% reduction in LDL-C results in an approximate reduction of 2.4% in MDS TBR. Further assume that 70% of the subjects will be on a statin and 30% will not be on a statin. From the results of the phase 3 evolocumab studies, a treatment effect of evolocumab QM over placebo in the percentage reduction in LDL-C at week 16 is assumed to be 55% for subjects who are not on a statin and 60% for patients who are on a statin. From the assumption that 10% of LDL-C reduction induces an approximate 2.4% of TBR reduction, we expect to observe a combined reduction of 14.0% in MDS TBR at week 16 in the evolocumab group compared to the control group. A combined standard deviation of 20.0% for the percentage change from baseline to week 16 is assumed for MDS TBR. After accounting for a dropout rate of 25%, the power is greater

than 90% for testing superiority of evolocumab over placebo on the percentage change in MDS TBR at week 16.

4. Study Endpoints and Covariates

4.1 Study Endpoints

4.1.1 Primary Endpoints

Percentage change from baseline in TBR within the MDS of the index vessel (right carotid, left carotid, or thoracic aorta) by FDG-PET/CT at week 16

4.1.2 Secondary Endpoints

[figure not shown]
- Percentage change in Lp(a) from baseline at week 16
- Percentage change in LDL-C from baseline at week 16
- Percentage change in ApoB from baseline at week 16

4.1.3 Safety Endpoints

Subject incidence of treatment-emergent adverse events compared to placebo for the duration of the study

4.1.4 Exploratory Endpoints

CCI

4.2 Planned Covariates

No covariate is planned.

5. Hypotheses and/or Estimations

The primary statistical hypothesis is as follows:

The null hypothesis is that there is no difference in the mean percent change from baseline at week 16 in TBR within the MDS of the index vessel between evolocumab and placebo, and the alternative hypothesis is that a mean difference does exist.

6. Definitions

6.1 Study Time Points

Enrollment Date

Enrollment Date is the same as Randomization Date.

Randomization Date

The date a subject is randomized in the interactive voice response system (IVRS)/interactive web response system (IWRS) as recorded on the eCRF.

First Dose Date of Investigational Product

For each subject, the First Dose Date of Investigational Product (IP) is defined as the first administration date of IP (evolocumab or placebo) as recorded on the IP administration eCRF.

Study Day 1

For each subject, Study Day 1 is defined as the first day that protocol-specified investigational product is administered to the subject. If a subject is randomized but never received IP, Study Day 1 is defined as the Randomization Date.

Study Day

For each subject, and for a given date of interest, Study Day is defined as the number of days since Study Day 1:

Study Day = (date of interest – Study Day 1 date) + 1.

If the date of interest is prior to the Study Day 1:

Study Day = (date of interest – Study Day 1 date), so that the day prior to Study Day 1 is study day -1.

Last Dose Date of Investigational Product

For each subject, the Last Dose Date of Investigational Product is defined as the date of the last administration of IP (evolocumab or placebo).

End of Study (EOS) Date

For each subject, the End of Study Date is the date recorded on the End of Study eCRF.

Study End Date

The Study End Date is the last EOS date of all randomized subjects.

6.2 Demographics and Baseline Related Definitions

Age

Age will be calculated or collected as the subject's age in years at enrollment as recorded on the eCRF.

Baseline Lipid and Lipid-related Parameters

Baseline values for fasting lipids (total cholesterol, HDL-C, LDL-C, VLDL-C and triglycerides), ApoA1, ApoB, CRP, Lp(a) and their derived parameters (eg, ratio between them) are defined as the mean of the two most recent non-missing fasting concentrations measured through central lab prior to or on Study Day 1. If for any reason only 1 value is available, then that value will be used as the baseline.

Other Baseline Values

For HbA1c and all other variables, the baseline value is defined as the last non-missing value collected prior to or on Study Day 1.

Change (absolute change) from Baseline

The arithmetic difference between a post-baseline value and baseline for a given time point:

Change (absolute change) from baseline = (post-baseline value – baseline value)

Percent Change from Baseline

The percent change from baseline for a given variable at a given time point is defined as: $100\% \times [(\text{value at given time point} - \text{baseline value}) / \text{baseline value}]$

Baseline CHD Risk Factors

A subject will be categorized as having 2 or more CHD Risk Factors (Y/N) from the list of the modified NCEP ATP III risk factors:

- current cigarette smoking
- hypertension
- type II diabetes mellitus
- family history of premature CHD as recorded on the eCRF
- low HDL-C defined as baseline HDL-C < 40 mg/dL in men and < 50 mg/dL in women.

Baseline National Cholesterol Education Program (NCEP) Risk Categories

Risk Factor	Defining Level
High Risk: CHD or CHD Risk Equivalent	Coronary Artery Disease OR Cerebrovascular or Peripheral Vascular Disease OR Type 2 Diabetes Mellitus OR 2 or more Risk Factors (see below) AND FRS > 20% (see Appendix A for FRS calculation)
Moderately High Risk	NOT High Risk AND 2 or more Risk Factors AND FRS \geq 10% AND \leq 20%
Moderate Risk	NOT High Risk AND 2 or more Risk Factors AND FRS < 10%
Lower Risk	NOT High Risk AND 0 to 1 Risk Factor

Risk Factors for NCEP Risk Categories:

Risk factors are: current cigarette smoking, hypertension or (baseline SBP \geq 140 or DBP \geq 90 mmHg), family history of premature CHD as recorded in the eCRF form, low HDL-C cholesterol defined as baseline HDL-C < 40 mg/dL, age \geq 45 years in men or \geq 55 years in women.

Risk Classification According to ESC/EAS Guidelines

The Systematic Coronary Risk Estimation (SCORE) system estimates the 10 year risk of a first fatal atherosclerotic event, whether heart attack, stroke, or other occlusive arterial disease, including sudden cardiac death (ESC/EAS 2011). The SCORE risk estimates will be computed from the high and low risk region tables based on sex and baseline smoking status, systolic blood pressure, total cholesterol and age. Risk classification of very high, high, moderate and low risk will be according to the ESC/EAS guidelines.

6.3 Other Study Related Definitions

Analytical Study Week Assignments

Analytical windows will be used to assign parameter measurements to study weeks. The algorithm is provided in [Appendix B](#).

Actual Treatment Group

A subject's actual treatment group is the randomized treatment group, unless the subject receives treatment throughout the study that is different than the randomized treatment group assignment, in which case the actual treatment group is the treatment received.

Investigational Product (IP)

IP includes SC evolocumab 420 mg QM and its corresponding SC placebo.

IP Exposure Period in Months

IP Exposure in Months = [min (Last Dose Date of IP + 28 days, EOS Date) - Study Day 1 +1] / 365.25 * 12.

Study Exposure Period in Months

For each randomized subject, Study Exposure in Months = (EOS date – Enrollment Date + 1) / 365.25 * 12.

Treatment Emergent Adverse Event (TEAE)

Treatment emergent adverse events are adverse events occurring from the first dose of IP date up to and including 30 days after the last dose of IP date or the EOS date whichever occurs first. Adverse events will be considered as treatment emergent if answer to the question "Did event start before first dose of investigational product?" on the eCRF is not "Yes".

Treatment-Emergent Disease-Related event

Treatment emergent disease-related events are events categorized as Disease-related Events (DREs) starting on or after first dose of investigational product and up to and including the end of study.

LDL-C Reflexive Approach

For all analyses related to LDL-C, unless specified otherwise, a LDL-C reflexive approach will be used. When calculated LDL-C is less than 40 mg/dL or triglycerides > 400 mg/dL, the UC LDL-C value from the same blood sample will be used instead, if available.

7. Analysis Subsets

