#### **6.2.1.2 Dosage Adjustments, Delays, Rules for Withholding or Restarting, Permanent Discontinuation**

No dose adjustments are allowed in this study. If, in the opinion of the investigator, a subject is unable to tolerate a specific dose of IP, that subject will discontinue IP but will continue to return for all other study procedures and measurements until the EOS.

If a subject is late for administration of IP, administration should occur as soon as possible. A dose of IP should not be administered within less than 7 days of a previous dose. If a subject arrives for a visit with IP administration and IP was administered within the prior 7 days, the dose should not be administered but all other study procedures should be conducted. Administration of IP should occur as soon as possible but at least 7 days after the previous administration. Subjects who completely miss a dose of IP will continue in the study and receive the next dose of IP per their schedule of administration.

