### 7.2.3 Treatment

Visits will occur per the Schedule of Assessments ([Table 1](#)) during the treatment period from day 1 (week 1, baseline) through week 12. Visits during the treatment period must be completed within  $\pm$  7 days of the target visit date.

Evolocumab/placebo is to be administered at the site after blood draw procedures. IP administration should be the last procedure to be performed during each visit.

If a subject withdraws from the study early, all efforts should be made to complete and report the observations as thoroughly as possible up to the date of withdrawal. The procedures for the EOS visit should be completed at the time of withdrawal ([Section 7.2.4](#)).

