#### **9.2.2 Adverse Events**

##### **9.2.2.1 Reporting Procedures for Adverse Events That do not Meet Serious Criteria**

The investigator is responsible for ensuring that all adverse events observed by the investigator or reported by the subject that occur from the signing of the ICF through the EOS visit are reported using the Event CRF.

The investigator must assign the following adverse event attributes:

- Adverse event diagnosis or syndrome(s), if known (if not known, signs or symptoms),
- Dates of onset and resolution (if resolved),
- Severity (and/or toxicity per protocol),
- Assessment of relatedness to IP (evolocumab/placebo and/or the AI/Pen), or other protocol-required therapies/protocol-required procedure or activity, and
- Action taken.

The adverse event grading scale used will be the CTCAE. The grading scale used in this study is described in [Appendix A](#).

The investigator must assess whether the adverse event is possibly related to the IMP (evolocumab or placebo) and/or the investigational device (AI/Pen). This relationship is indicated by a “yes” or “no” response to the question: “Is there a reasonable possibility that the event may have been caused by the IMP (evolocumab or placebo) and/or the investigational device (AI/Pen)?”

The investigator must assess whether the adverse event is possibly related to use of the investigational device (AI/Pen) or any study-mandated activity (eg, administration of IP, protocol-required therapies, device(s) and/or procedure [including any screening procedure(s)]. This relationship is indicated by a “yes” or “no” response to the question: “Is there a reasonable possibility that the event may have been caused by a study activity (eg, administration of IP, protocol-required therapies, device(s)), and/or procedure?”

---

If the severity of an adverse event worsens from the date of onset to the date of resolution, record a single event for each increased level of severity on the Event CRF.

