#### **9.2.2.2 Reporting Procedures for Serious Adverse Events**

The investigator is responsible for ensuring that all serious adverse events observed by the investigator or reported by the subject that occur after signing of the ICF through 30 days after the last dose of IP or the EOS visit, whichever is later, are recorded in the subject's medical record and are submitted to Amgen. All serious adverse events must be submitted to Amgen within 24 hours following the investigator's knowledge of the event via the Event CRF.

The investigator must assess whether the serious adverse event is possibly related to any study-mandated activity or procedure. This relationship is indicated by a "yes" or "no" response to the question: "Is there a reasonable possibility that the event may have been caused by a study activity/procedure?"

The investigator is expected to follow reported serious adverse events until stabilization or reversibility.

New information relating to a previously reported serious adverse event must be submitted to Amgen. All new information for serious adverse events must be sent to Amgen within 24 hours following knowledge of the new information. The investigator may be asked to provide additional follow-up information, which may include a discharge summary or extracts from the medical record. Information provided about the serious adverse event must be consistent with that recorded on the Event CRF.

If a subject is permanently withdrawn from protocol-required therapies because of a serious adverse event, this information must be submitted to Amgen.

---

To comply with worldwide reporting regulations for serious adverse events, the treatment assignment of subjects who develop serious, unexpected, and related adverse events may be unblinded by Amgen before submission to regulatory authorities. Investigators will receive notification of related serious adverse events reports sent to regulatory authorities in accordance with local requirements.

Amgen will report serious adverse events and/or suspected unexpected serious adverse reactions as required to regulatory authorities, investigators/institutions, and IRBs/IECs in compliance with all reporting requirements according to local regulations and good clinical practice (GCP).

The investigator is to notify the appropriate IRB/IEC of serious adverse events occurring at the site and other adverse event reports received from Amgen, in accordance with local procedures and statutes.

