#### **10.5.4 Safety Endpoints**

The current Medical Dictionary for Regulatory Activities version at the time of the data lock will be used to code all adverse events to a system organ class and a preferred term.

Subject incidence of all treatment emergent adverse events will be tabulated by system organ class and preferred term. Tables of fatal adverse events, serious adverse events, adverse events leading to withdrawal from IP, device-related adverse events, and significant treatment-emergent adverse events will also be provided. Subject incidence of disease-related events and fatal disease-related events will be tabulated by system organ class and preferred term. Subject-level data may be provided instead of tables if the subject incidence is low.

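### The SAP's TEAE window closes 30 days after the last dose, so late non-serious AEs in subjects who stay on study off IP are collected but not tabulated, although the safety endpoint covers the whole study

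*SAP*

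**What the plan says.** - **Window.** SAP 6.3 opens the TEAE window at the first dose of IP and runs it "up to and including 30 days after the last dose of IP date or the EOS date whichever occurs first". The next sentence begins "Adverse events will be considered as treatment emergent if answer to the question" and turns on an eCRF item asking whether the event began before first dose. It gives no end date.
- **Neighbouring definition.** Also in SAP 6.3, treatment-emergent disease-related events (DREs) run from first dose to end of study, with no cut tied to the last dose.
- **Endpoint.** SAP 4.1.3 gives a single safety endpoint: "Subject incidence of treatment-emergent adverse events compared to placebo for the duration of the study". Protocol 10.1.1.3 agrees.
- **Collection.** Protocol 9.2.2.1 requires that adverse events that "occur from the signing of the ICF through the EOS visit are reported using the Event CRF". For SAEs, Protocol 9.2.2.2 extends collection "through 30 days after the last dose of IP or the EOS visit, whichever is later".
- **Follow-up off drug.** Under Protocol 6.2.1.2, a subject who stops IP for intolerance "will continue to return for all other study procedures and measurements until the EOS", and a subject who misses a dose stays in the study. Protocol 8.1 lets a subject decline IP and remain. For those who leave altogether, Protocol 7.2.3 says: "The procedures for the EOS visit should be completed at the time of withdrawal".
- **Tables.** SAP 10.6.1 restricts its overall summaries to TEAEs. In the tables by system organ class and preferred term, it applies the qualifier to all events but not to serious events or to those leading to IP withdrawal. Protocol 10.5.4 likewise plans "Tables of fatal adverse events, serious adverse events, adverse events leading to withdrawal from IP, device-related adverse events" without the qualifier.

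**The concern.** The endpoint wording covers the study, and the collection rules deliver data to EOS even for subjects no longer dosed. The derivation then discards part of that data for exactly those subjects. The same SAP section treats disease-related events differently, so two kinds of treatment-emergent event are counted over different periods with no stated reason.

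The difference can also split similar events. Protocol 9.1.1 says a disease-related event judged worse than expected, or related to study treatment, is reported as an AE or SAE. A late vascular event would be counted while classed as a DRE, but would fall outside the TEAE window once reclassified.

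At stake is the completeness of the only safety endpoint in subjects who stopped dosing, a group whose later course a safety reader would want to see.

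**Working it through.** **Inputs.** SAP Appendix B sets visit day = 7 × week + 1. This gives 29, 57, 85 and 113 for weeks 4, 8, 12 and 16, matching the days printed there. Protocol 6.2.1.1.2 places doses on Day 1 and at weeks 4, 8 and 12, each of the last three ± 7 days. Protocol Table 1 allows EOS at week 16 minus up to 7 days, which is Day 106 to 113.

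**Formula.** With last dose on day L and EOS on day E, the window ends at min(L + 30, E). On-study days outside it = max(0, E − (L + 30)).

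| Last dose (range) | On schedule, E = 113 | Share of Days 1–113 | Across visit windows |
|---|---|---|---|
| Day 1 | 113 − 31 = 82 | 73% | 106 − 31 = 75 to 82 |
| Day 29 (22–36) | 113 − 59 = 54 | 48% | 106 − 66 = 40 to 113 − 52 = 61 |
| Day 57 (50–64) | 113 − 87 = 26 | 23% | 106 − 94 = 12 to 113 − 80 = 33 |
| Day 85 (78–92) | 85 + 30 = 115 > 113, so 0 | 0% | 0 to 113 − 108 = 5 |

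A subject who only misses the week 12 dose and stays on study falls in the Day 57 row. With a window through EOS, every entry would be zero.

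**Which events are lost.**
- A late DRE is counted, because its window runs to end of study.
- A late SAE may appear in the table of serious events that lacks the treatment-emergent qualifier, although the SAP does not say so.
- A late event that itself ended dosing could appear in the withdrawal table, which also lacks the qualifier.
- The remaining late events, non-serious and not disease-related, are collected but have no table.

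**After EOS.** SAE collection runs to the later of the two dates and the TEAE window to the earlier. The gap is max(0, L + 30 − E). On schedule it is 115 − 113 = 2 days. Across the week 12 and EOS visit windows it runs from 0 to 92 + 30 − 106 = 16 days. It concerns SAEs only.

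**Effect on incidence.** This cannot be computed, because the documents do not say how many subjects would stop IP early and stay on study. The 25% dropout in SAP 3.2 is a sample-size allowance, not that rate. As a scale only: with 60 subjects planned per arm, one subject whose sole adverse event falls outside the window moves that arm's overall incidence by 1/60 = 1.7 points.

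**The case against.** The strongest reply is that the endpoint concerns treatment-emergent events, not all on-study events. The protocol sets no end date for that term, so the SAP is entitled to supply one. Last dose + 30 days covers the monthly dosing interval, resembles the exposure definition in the same section (last dose + 28 days, capped at EOS), and is a recognised on-treatment convention. **This largely stands.** The window is legitimate as an on-treatment analysis. The weakness is that it is the only planned one, beside an endpoint worded for the whole study and a DRE window that runs to end of study.

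It can also be said that late events are off-drug. That is fair, but the protocol does not treat 30 days as a general end of follow-up interest. Protocol 7.5.1 discourages non-protocol lipid testing until at least 12 weeks after the last dose, and Protocol 9.3 asks for pregnancy reports through 15 weeks. Neither shows that late AEs are drug-related.

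The impact is limited as well. Subjects who stopped for intolerance will often already have a counted event. Early withdrawers have EOS brought forward and lose little or nothing before EOS.

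Three stronger readings are tempting, and the documents do not support them:

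- **That the two sentences of the TEAE definition compete, so the count depends on which is programmed.** The eCRF item asks only whether the event began before first dose. It can settle the start boundary and nothing else. What is missing is a clarifying clause.
- **That a lost event could decide whether a preferred term enters the table with the 1% cut-off.** At about 60 per arm a single subject is already 1.7%, so the cut-off filters nothing, and all TEAEs are tabulated by preferred term anyway.
- **That the post-EOS SAE gap is a material loss.** A reporting period and a tabulation window need not match, and events after EOS lie outside a study-duration endpoint. The on-schedule gap is 2 days, and such SAEs may already be covered by the serious-event table. The range of 0 to 16 days describes possible schedules, not how often they occur.

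**Conclusion.** The concern holds as a minor mismatch. The TEAE window is narrower than the endpoint wording, the collection period and the adjacent DRE window. The loss is confined to non-serious, non-disease-related events starting more than 30 days after the last dose in subjects who remain on study: 82, 54 or 26 days for a last dose on Day 1, 29 or 57 with EOS on Day 113, and at most 5 days for a week 12 dose within its visit window.

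This rests on the TEAE tables using the stated end date and on subjects off IP being followed to EOS as the protocol provides. The practical effect is probably small, because safety is descriptive and completers are almost untouched. Its size in events or incidence is unknown. The documents give no basis for saying that the safety comparison between arms would be biased in either direction.

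**What to change.** Amend the SAP before unblinding:

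1. Tabulate adverse events with onset from first randomised dose through EOS, in line with the endpoint wording and the DRE window.
2. Keep the present last dose + 30 days window as an on-treatment table beside it.
3. State in SAP 6.3 that the eCRF question decides only the start boundary.
4. List any SAE collected after EOS but within 30 days of the last dose, and label in SAP 10.6.1 which tables are limited to TEAEs and which cover all SAEs.

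The cost is a few lines of SAP text, one derivation flag, one extra table and one listing, all from data the protocol already collects. The downside is that a few off-drug events enter the through-EOS table. Showing the on-treatment table beside it lets the reader separate them.
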